### 5.4 Sensitivity Analysis

When missing data are suspected to be *missing not at random*, any standard analysis of the available cases is likely biased. The bias cannot be corrected since missingness depends on unobserved data and therefore cannot be empirically modelled reliably. We will therefore assess the sensitivity of inferences made from missing data by imputing missing data under both pessimistic and optimistic scenarios and repeating the TMLE algorithm to provide bounds on the statistical uncertainty. The characteristics of non-responders will be summarized, and we will present the heterogeneity of the treatment effect due to missing data.

## 6. Sample Size and Accrual

With recruitment of 572 participants, this study has  $>0.80$  statistical power to detect small differences in QOL between treatment approaches (Cohen's  $d = 0.24$ , or 5.5 points on the physical function scale of EORTC-QLQ-C30). Power analyses conservatively allowed for 10% missing data and assumed a correlation between repeated QOL measurements of 0.3. Assuming a similar balance of treatments within subgroups, this study also has  $>0.80$  power to detect moderate but clinically important treatment effects (Cohen's  $d = 0.43$ , or 9.9 points on the physical function scale of EORTC-QLQ-C30) within subgroups as small as 30% of the study cohort. Anticipated subgroups of this size include patients aged 75 years or older, women, and patients with multiple comorbid health conditions. For the secondary outcome of bladder cancer-specific mortality, data from a review combining multiple trials demonstrated an anticipated 1-year bladder cancer-specific mortality rate of 4.8% when treated with medical management. Assuming a 4.8% mortality rate in the medical management arm, this study has power to detect differences in 1-year bladder cancer-specific mortality rates of  $\leq 1\%$  in the radical cystectomy arm (power  $> 80\%$ ).

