9.4 Sample Size and Statistical Power

We aim to recruit from a heterogeneous patient population that will allow for rich and broadly applicable estimation of outcomes and experiences after NMIBC that recurs after first-line BCG. **We will enroll up to 900 participants across a broad geographic recruitment area.** This cohort would represent the largest pragmatic study of recurrent high-grade NMIBC patients to date. The total sample size for CISTO is primarily motivated by statistical power considerations for **Aim 1**, comparing QOL between patients treated with medical management versus radical cystectomy. Presently, there are no guiding documents

on directly using TMLE in the calculation of statistical power for designing an observational study. The variance of the treatment effect estimate—and thus power—is a complicated function of the number treated in each group, the potential and observed outcomes, and the covariate-based probabilities of treatment with radical cystectomy. The 2:1 recruitment ratio of medical management to radical cystectomy patients at each CISTO site will ensure at least a 33% rate of radical cystectomy in the CISTO study population. However, based on actual rates of enrollment of cystectomy patients, we motivated the study sample size of 572 using 40.9% cystectomy patients in a standard two-sample repeated measures approach that will be less efficient than the analytic methods used at the time of data analysis.

Statistical power was fixed at 0.80 throughout and we considered two-sided tests with alpha=0.05 indicating statistical significance, with no adjustment for multiple comparisons for the primary question of interest. Correlation between repeated measures was assumed to be 0.3, an estimate we have observed in numerous other QOL studies. Minimal detectable effect sizes (units of QOL standard deviation) are reported in **Table 3** below for Aim 1 within subgroups with varying prevalence.

Table 3. Minimal Detectable Effect Sizes

		Subgroups		
		50%	30%	20%
Aim 1: Patient QOL	Overall	0.24	0.34	0.44

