Aim 2 is largely descriptive in nature and no statements of statistical power were considered. With recruitment of 572 patient participants, anticipating 235 radical cystectomy patients and 337 patients treated with medical management in Aim 1 and conservatively allowing for 10% missing data, this study has >0.80 statistical power to detect small differences in QOL between treatment approaches (Cohen's $d = 0.24$)²⁰ that are well below the minimally important difference of 0.5. Assuming a similar balance of treatments within subgroups, this study has >0.80 power to detect moderate but clinically important effect sizes (Cohen's $d = 0.43$) within subgroups as small as 30% of the study cohort. From SEER, large treatment effect differences would be detectable in subgroups of gender (20% female), age (52% over 75), comorbid health conditions (22% Charlson Index 1 or greater), and CIS (25%). We will plan a subgroup analysis for patients receiving investigational agents as part of a phase III clinical trial if at least 10% of participants in the medical management arm are in a trial. To inform power calculations for our secondary outcomes of bladder cancer-specific mortality, we used data from a microsimulation model demonstrating low anticipated 1-year mortality event rates (0.8% for radical cystectomy, 3.6% for continued medical management). We would have 69% power to detect a similar difference in one-year mortality due to bladder cancer and 80% power to evaluate the difference between study arms in 2-year bladder cancer-specific mortality.

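### SAP section 6 counts women among subgroups of at least 30% with more than 0.80 power at d = 0.43; the only documented share, 20%, gives power of about 0.61

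*SAP*

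**What the plan says.** SAP section 6 bases power on 572 participants, 10% missing data and a correlation of 0.3 between repeated measurements. It claims power above 0.80 for d = 0.24 (5.5 points) overall and for d = 0.43 (9.9 points) "within subgroups as small as 30% of the study cohort". The next sentence applies this to named groups: "Anticipated subgroups of this size include patients aged 75 years or older, women, and patients with multiple comorbid health conditions". It gives no prevalence for any of them.

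Protocol section 9.4 uses the same 572 patients (235 cystectomy, 337 medical management) and makes the same claim of d = 0.43 at 30%. It then treats the named subgroups separately and more cautiously: "From SEER, large treatment effect differences would be detectable in subgroups of gender (20% female), age (52% over 75", and, in the same list, "comorbid health conditions (22% Charlson Index 1 or greater". It also describes the overall detectable effect as "well below the minimally important difference of 0.5".

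SAP section 4.1.1 makes gender a planned subgroup, and Hypothesis 1.3 in both documents names women first.

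**The concern.** A subgroup of 20% lies below the 30% floor that the SAP sets for its own power claim. The protocol keeps two tiers apart: moderate effects in subgroups of 30% or more, and only large effects in the SEER list that includes women. The SAP moves women into the first tier without giving a figure to justify it.

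At stake is how the gender result will be read. Someone relying on SAP section 6 would put the chance of missing a true 9.9-point effect in women below 20%. If women are 20% of the cohort, that chance is about 39%, and a null result in women could be taken as evidence against an important difference when the study was not large enough to show one.

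The comorbidity group has a related problem. Neither document defines it or gives its prevalence. The nearest figure, 22% with Charlson 1 or greater, describes a different group.

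**Working it through.** **Inputs.** From protocol 9.4 and SAP 6: 235 and 337 patients per arm, two-sided alpha 0.05, power 0.80, 10% missing, correlation 0.3, the same treatment balance within subgroups, women 20%. The SD implied by SAP 6 is 5.5 / 0.24 = 22.9 points.

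**Model (assumed).** The documents give no formula. I used a two-sample t-test on the 12-month score with the variance multiplied by 1 − 0.3² = 0.91, as for baseline adjustment. For a subgroup of share f:

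- n₁ = 235 × f × 0.9 and n₂ = 337 × f × 0.9
- SE in SD units = √[0.91 × (1/n₁ + 1/n₂)]

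**Reproducing the plan's figures.** The effects detectable with 0.80 power are:

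| Share | n₁ / n₂ | Detectable d |
|---|---|---|
| 100% | 211.5 / 303.3 | 0.240 |
| 50% | 105.8 / 151.7 | 0.340 |
| 30% | 63.5 / 91.0 | 0.440 |

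These are the three values in protocol Table 3. The columns of that table have lost their alignment in the extracted text, and 0.44 can seem to sit under 20%. The match above, and the protocol's own 0.43 at 30%, show that 0.44 belongs to 30%. Two other readings of the repeated-measures approach do not reproduce d = 0.24 overall and were set aside: a change score gives power of 0.62 to 0.67 there, and the mean of four follow-ups gives about 0.99.

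**Women at 20%.** 0.20 × 572 = 114 women (47 cystectomy, 67 bladder-sparing), against 0.30 × 572 = 172. After 10% missing, n₁ = 42.3 and n₂ = 60.7, and SE = √[0.91 × (1/42.3 + 1/60.7)] = 0.191. Variant B assumes no missing data. Variant C drops the correlation factor.

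| Quantity | Model | B | C |
|---|---|---|---|
| Power at d = 0.43, share 30% | 0.782 | 0.823 | 0.743 |
| Power at d = 0.43, share 20% | 0.606 | 0.652 | 0.566 |
| Power at d = 0.50, share 20% | 0.736 | 0.781 | 0.696 |
| Detectable d, share 20% | 0.541 | 0.512 | 0.567 |
| The same in points (× 22.9) | 12.4 | 11.7 | 13.0 |
| Share needed for 0.80 at d = 0.43 | 31.4% | 28.2% | 34.4% |
| Patients needed, of 572 | 179 | 162 | 197 |

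The shortfall from 0.80 to 0.61 has two parts. About 0.02 arises because the model's value at 30% is 0.44 rather than 0.43 (power 0.78). About 0.18 comes from the lower share.

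**Check without a variance model.** Take the SAP's claim as exactly 0.80 at d = 0.43 and 30%, and scale by the square root of the share (normal approximation):

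- (1.960 + 0.842) × √(0.20/0.30) − 1.960 = 0.328, which gives power 0.63
- detectable d = 0.43 × √(0.30/0.20) = 0.527, or 12.1 points

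For a 20% subgroup to reach 0.80, power at 30% would have to be about 0.93.

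**The other named groups.** Age over 75, at 52%, has power of about 0.95 (0.93 to 0.97). If the 22% Charlson figure applied to the comorbidity group, power would be about 0.65 (0.61 to 0.69). This is only illustrative, because the groups differ.

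**The case against.** The strongest reply is that 20% is a registry figure and may be out of date. The SAP carries the same date as the data freeze, which takes in all baseline data, so its authors could have known the enrolled share of women. The protocol had already revised the cystectomy share "based on actual rates of enrollment of cystectomy patients". On the same model, power at d = 0.43 rises to 0.70 at 25% women and 0.78 at 30%, and at 25% the detectable effect is 0.48 SD, just below 0.5. This stands as a limit on the finding: the 0.61 is conditional on 20%. It does not rescue the sentence, because neither document reports an enrolled share of women.

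A second reply is efficiency. The protocol calls its planning method "less efficient than the analytic methods used at the time of data analysis", but it gives no size for the gain. At 20% women, reaching 0.80 at d = 0.43 would need the variance cut by 1 − (0.43/0.541)² = 37% (30% to 42% across the variants).

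Third, the protocol's own statement about women is sound: it promises only large effects, and power at d = 0.8 and 20% is about 0.99. Table 3, introduced as showing effects "below for Aim 1 within subgroups with varying prevalence", may also have held a 20% value that was lost in extraction. Both points are fair. They place the fault in one sentence of the SAP, not in the protocol's planning, and they make the two documents harder to reconcile.

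Finally, the protocol allows enrolment of up to 900, which would give roughly 0.77 to 0.85 at 20% with 40.9% cystectomy. Both documents, however, base their power statements on 572.

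**Conclusion.** The SAP sentence is wrong as written: it gives women a power that the documents' only prevalence figure does not deliver. At 20% women, power at d = 0.43 is about 0.61 (0.57 to 0.65), or 0.63 when scaled from the SAP's own claim alone. The detectable effect of about 0.54 SD (0.51 to 0.57) exceeds the 0.5 that the protocol calls minimally important, although the margin is small.

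These figures rest on the 20% share, on 572 patients, on a treatment split in women like that of the whole cohort, and on a variance model inferred because it reproduces the plan's detectable effects. An enrolled share of about 31% women (28% to 34%) would make the claim true, and the documents do not exclude it. The comorbidity entry is unsupported because the group is undefined; no power can be assigned to it. The primary comparison, at d = 0.24 overall, is unaffected.

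**What to change.** Reconcile SAP section 6 with protocol section 9.4.

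- **Women:** cite the enrolled proportion if it supports 30%. Otherwise remove women from the list and state the detectable effect at their actual share, calculated with the sponsor's own method. At 20% this should come to about 0.54 SD, or 12.4 points.
- **Comorbidity:** define the group and give its prevalence, or remove it from the list.
- **Age:** this entry can stay.

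The cost is two or three sentences in SAP section 6, with no change to the primary analysis. The stated subgroup power becomes less favourable unless enrolment data support the 30%.

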## 7. Data Monitoring

We will monitor the accuracy of data entry by the sites both internally and externally. We will review study data on arrival for completeness. We will then subject each submitted data set to a set of preliminary checks to search for values that are out-of-range or otherwise inappropriate. The DCC will set up in-line data quality checks within the data entry system, which will check for missing information, inconsistencies, and logic errors. The CCC and DCC will monitor this information on a regular basis. In addition, the DCC will perform quality assurance checks by running regular data quality reports. These reports include missing values for required fields, incorrect data type, range checks, outliers, hidden fields that contain values, and multiple-choice fields with invalid values. Values that need to be corrected will be brought to the attention of the research staff at

that site. The DCC and CCC will investigate any discrepancies or unexpected values that were discovered through the regular report or through visual inspection.

## 8. Data and Safety Monitoring Plan (DSMP)

The CISTO Study adheres to a Data Safety Monitoring Plan. Given the minimal risk nature of this observational cohort study, monitoring is conducted by the study's Executive Committee. On a monthly basis, the Executive Committee reviews any data and safety events and procedures and determine recommendations for these events and procedures as appropriate, including identifying, reviewing, and reporting adverse events (AEs) and serious adverse events (SAEs) and unanticipated problems to the applicable Institutional Review Boards (IRBs) or other monitoring bodies. SAEs are defined as 1) death during the study period; 2) life-threatening event related to the treatment or significant disability/incapacity related to the treatment; 3) inpatient hospitalization (other than for cystectomy); and 4) prolonged hospitalization following cystectomy (14 days or more). The number of adverse events and related unexpected serious adverse events (SAEs) will be summarized by arm, by recruitment site, by grade, and by the National Cancer Institute's Common Terminology Criteria for Adverse Events (CTCAE) system organ class. In addition, for each toxicity, the proportion of affected participants overall and by arm will be summarized by the maximum CTCAE grade experienced. The interim review of SAEs will not lead to recommendations towards study recruitment or discontinuation.

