9.0 Statistical Analysis Plan

9.1 Delineation of Treatment Arms

We will use block recruitment within practice sites, no more than two thirds of whom within each completed block may be medical management patients. Using block recruitment ensures that the study will be sufficiently well balanced to adequately characterize the effect of each treatment relative to the other and maintain power to evaluate primary and secondary outcomes. Each treatment arm is defined by each patient's choice of treatment at enrollment. If a patient ultimately receives a different treatment from what they chose initially, this is considered as an outcome of their initially chosen treatment. We expect that all or almost all patients who choose radical cystectomy will receive it prior to evaluation of the primary endpoint at 12 months post-enrollment, while up to 20% of patients who choose medical management may undergo radical cystectomy during this period.

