10.1 SAE Reporting

Participants will be monitored for SAEs throughout their study surveillance period (enrollment through up to four-year follow-up). The occurrence of an SAE may come to the attention of study personnel during study follow-up phone interview, by UW study staff personnel conducting follow-up, or by a study participant calling the study team or presenting for medical care. If an SAE comes to the attention of study personnel via patient, caregiver, or family report, the site research coordinator will be notified that an SAE form needs to be completed. The site research coordinator will then use the EMR to fill out the SAE form. The site PI will then complete the form and sign the form. The SAE form will then be submitted to the DCC who will provide it to the CISTO Executive Committee. The CISTO Executive Committee will review the SAE form and ask the site PI for additional clarification or specification as they see necessary.

SAEs are defined as one of the following conditions:

1. Death during the period of protocol-defined surveillance;
2. Life-threatening event related to the treatment or significant disability/incapacity related to the treatment;
3. Inpatient hospitalization (other than for cystectomy);
4. Prolonged hospitalization following cystectomy (14 days or more).

All SAEs will be:

1. Recorded on the SAE case report form;
2. Followed until satisfactory resolution or until the study investigators deem the event to be chronic or the participant to be stable;
3. Reported to the study investigators, the project managers, and site IRBs per their reporting guidelines.

CISTO is an observational study using procedures or treatments with well-established risk profiles. There is no reason to suspect the risk profiles in the proposed study population would differ. The number of adverse events and related unexpected serious adverse events (SAEs) will be summarized descriptively by arm, by grade and body system. The proportion of participants experiencing each toxicity will be summarized by maximum National Cancer Institute's Common Terminology Criteria for Adverse Events (NCI CTCAE) grade²¹ experienced, overall and by arm.

The local and systemic side effects associated with intravesical therapy will be graded according to the International Bladder Cancer Group's (IBCG) recommendations²² (percentage indicates incidence rate):

- Cystitis noninfective (33-80%)

- Hematuria (up to 90%)
- Urinary tract obstruction (rare)

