## 4.3 As-Treated Analyses

Patients who choose a treatment arm upon enrollment may ultimately be treated as intended or may have first received treatment of the other arm, or treatment may be delayed or postponed. For as-treated analyses, we will classify participants' treatment arm according to the first treatment observed within six months of enrollment (BST, radical cystectomy, or none observed within six months). Patients with no bladder cancer treatment observed within six months will be excluded from as-treated analyses directly comparing BST to radical cystectomy. Outcomes and characteristics of patients with no treatment observed will be presented and informally compared to the as-treated groups. The statistical

approach with the as-treated groups will otherwise mimic ITT analyses. Results from the ITT analysis will be considered primary, with as-treated analyses considered secondary.

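### Toxicity is compared between treatments only by arm, which SAP 8 does not define for safety; on the natural reading, complications of later cystectomy are tabulated under bladder-sparing therapy

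*SAP*

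**What the plan says.** SAP 8 gives two safety summaries. The first counts adverse events, and those serious adverse events that are related and unexpected, within arm, site, grade and CTCAE organ class. The second is a proportion of patients: "for each toxicity, the proportion of affected participants overall and by arm will be summarized by the maximum CTCAE grade experienced". Protocol 10.1 plans the same kind of display, by arm, grade and body system. Neither section defines arm for this purpose.

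The general definition is in Protocol 9.1: "Each treatment arm is defined by each patient's choice of treatment at enrollment". The same section settles what happens after a switch: "If a patient ultimately receives a different treatment from what they chose initially, this is considered as an outcome of their initially chosen treatment". It also gives the expected size of the switch by 12 months: nearly all who choose cystectomy will have had it, "while up to 20% of patients who choose medical management may undergo radical cystectomy during this period". SAP 1.5 and 4.1 use the enrollment choice too, but there it is tied to the primary analysis.

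SAP 4.3 adds secondary as-treated analyses that classify patients "according to the first treatment observed within six months of enrollment". It does not mention safety. Surveillance for serious adverse events runs from "enrollment through up to four-year follow-up" (Protocol 10.1).

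Protocol 10.1 also lists expected events separately for intravesical therapy, pembrolizumab and cystectomy. It names a grading or reporting standard for each: the IBCG recommendations, earlier published reports, and Clavien-Dindo.

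**The concern.** A table by chosen arm answers one question: what happens to patients who set out on this strategy? A reader of a table labelled as toxicity is likely to ask another: what are the side effects of this treatment? The two answers separate when a material share of one arm goes on to receive the other arm's treatment.

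Take a patient who chooses bladder-sparing therapy, starts it, has a cystectomy at month 8 and then develops ileus or a thromboembolic event. On the enrollment-choice reading, that event is counted under bladder-sparing therapy. Reporting the maximum grade adds to this, because a more severe postoperative event replaces an earlier, milder event of the same type. A readmission for a surgical complication also falls under the general hospitalization item of the serious adverse event definition, not under the item for prolonged stay after cystectomy.

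This matters because the study is meant to help patients decide (Protocol 12.0), and its rationale weighs progression risk against surgical morbidity (Protocol 2.1). If the only between-treatment safety display mixes the two sources of harm, a reader cannot recover either one from it.

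**Working it through.** **Inputs**
- Anticipated arms: 235 cystectomy and 337 medical management, 572 in total (Protocol 9.4).
- Crossover from medical management to cystectomy by 12 months: up to 20% (Protocol 9.1). The documents give no lower or later figure, so 10% and 5% are shown as assumed alternatives.
- Listed cystectomy complication rates: gastrointestinal 29%, infectious 25%, thromboembolic 8% (Protocol 10.1).

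**Step 1: the plan's own split.** Protocol 9.4 states 40.9% cystectomy among 572: 0.409 × 572 = 233.9, against the stated 235 (235/572 = 41.1%). Also 235 + 337 = 572. The split is reproduced to within rounding.

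**Step 2: cystectomies inside the medical-management arm.** Number = crossover share × 337. Share of all cystectomies = number / (number + 235), taking all 235 who chose surgery to have had it.

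| Crossover | Number | Share of all cystectomies |
|---|---|---|
| 20% | 67.4 | 67.4 / 302.4 = 22.3% |
| 10% | 33.7 | 33.7 / 268.7 = 12.5% |
| 5% | 16.85 | 16.85 / 251.85 = 6.7% |

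**Step 3: events added to the medical-management arm.** Percentage points = crossover share × listed rate. Patients = points × 337.

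| Category | 20% crossover | 10% | 5% |
|---|---|---|---|
| Gastrointestinal (29%) | 5.8 points (19.5 patients) | 2.9 | 1.45 |
| Infectious (25%) | 5.0 points (16.9 patients) | 2.5 | 1.25 |
| Thromboembolic (8%) | 1.6 points (5.4 patients) | 0.8 | 0.4 |

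**Step 4: effect on the contrast.** Suppose bladder-sparing therapy itself caused no gastrointestinal events and all who chose cystectomy had it. At 20% crossover the chosen-arm table would then show 29 − 5.8 = 23.2 points, where a split by treatment received would show 29.

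**Step 5: does another planned analysis separate these events?**
- *As-treated rule (SAP 4.3).* A patient who chose bladder-sparing therapy but had cystectomy as the first treatment within six months would be moved. A patient who started bladder-sparing therapy and had surgery afterwards would not be. The rule is also not applied to safety anywhere in the documents.
- *Treatment-specific lists (Protocol 10.1).* These set grading and reporting standards, not the groups in which events are tabulated. Some terms, such as ileus or wound dehiscence, appear only on the cystectomy list. Urinary tract infection, urinary tract obstruction and hematuria appear on both the intravesical and the cystectomy lists, so the event term alone cannot separate those.

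**The case against.** The strongest reply is that the chosen-arm display is a declared design choice. Protocol 9.1 says of a switch that "this is considered as an outcome of their initially chosen treatment". For a patient deciding at enrollment, later surgery and its complications are part of what choosing bladder-sparing therapy entails. This stands. A reader might infer that the chosen-arm table is wrong and should give way to one by treatment received. The documents do not support that, and which of the two is shown first is a matter of preference.

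Four further points have force.

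- **Definition.** SAP 8 does not say which meaning of arm it uses, so enrollment choice is an inference from Protocol 9.1, although the natural one. This limits the claim, but it is also a reason to write the definition down.
- **Publication.** A reader might infer that a contaminated side-effect profile of bladder-sparing therapy will be published. The SAP sentence sits in the data and safety monitoring plan, adverse events are not among the listed secondary outcomes, and neither document says how these tables will be published.
- **Identifiability.** It would be too strong to say that surgical complications cannot be told apart. Many terms are specific to surgery, and Protocol 6.6 abstracts cystectomy, medical management and adverse events from the record. The gap is that no table is planned to use this information.
- **Attribution.** Assigning each event to the most recent treatment has its own error: delayed BCG or immunotherapy toxicity that appears after surgery would be counted as surgical. This stands, and the fix allows for it.

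**Conclusion.** The point holds as a cheap improvement, not as an error in the plan. By-arm summaries are the only between-treatment safety comparison planned; the overall, site, grade and organ-class summaries do not separate treatments. Arm is undefined for safety. On the natural reading, complications of later cystectomy fall under bladder-sparing therapy.

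The size is an upper bound: about 67 of 337 patients by 12 months, adding at most about 5.8, 5.0 and 1.6 points of gastrointestinal, infectious and thromboembolic events. At 5% crossover the gastrointestinal figure is about 1.5 points. The bound rests on these assumptions:

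- crossover reaches the protocol's 20% ceiling;
- switchers have the listed complication rates, which come from cited reports whose follow-up windows are not given here;
- no switcher already had an event in the same category, which is least secure for infections because urinary tract infection is on both lists;
- complications fall within the period tabulated.

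A reader might also infer that the effect grows over the four years of surveillance. It may, but the documents give no crossover figure beyond 12 months, so no size can be attached to that. The primary endpoint and its analysis are unaffected.

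**What to change.** In Protocol 10.1 and SAP 8:

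1. State that arm, for safety, is the choice at enrollment, and keep that table as the comparison of strategies.
2. Add a descriptive table of adverse events and serious adverse events by treatment received before onset: before any treatment, intravesical, systemic, and after cystectomy. Give the number treated and the person-time for each.
3. In that table, flag post-cystectomy events in patients who had earlier BCG or immunotherapy, so that delayed toxicity is not automatically assigned to surgery.
4. State that the SAP 4.3 first-treatment grouping is not relied on alone for toxicity.

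The cost is a few sentences and one extra set of tables. Protocol 6.6 already has the treatments and adverse events abstracted, and the six-month rule in SAP 4.3 already needs treatment timing. Adverse event onset dates are also needed; the documents do not say that these are recorded, so this is assumed and should be confirmed. The added table is descriptive, not a causal comparison, and should be labelled as such.
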